### Pre-Intervention Procedures

The study staff member will arrive at bedside, explain the risks and benefits of the study, and will obtain informed consent. Next, a physician or authorized study staff member will collect blood pressure and pulse data using standard sphygmomanometers in hospital wards, and will ask the patient to report current pain level on a 0 to 10 scale. We will also assess coping (Roberts, 2010) by asking "How are you coping with your labor?" We will also obtain all pain ratings collected and documented in the EHR during the current hospitalization up to 96 hours

before the intervention. Additionally, the study staff member will administer the **Quantitative Patient Survey** -- included at the end of this document and based on the NIH PROMIS Global Health Survey (10 items) and Childbirth Self-Efficacy inventory (15 items).

When a patient expresses interest in the study, she will then undergo randomization to either the VR arm or the Control arm of the study. Group assignments will be maintained inside sequentially numbered, sealed, opaque envelopes. After informed consent, study personnel will then open the assigned envelope and the study treatment will be revealed. Patients, providers, and study personnel will not be blinded to the assigned intervention.

For those patients randomized to VR, the study staff member will explain the use of the Samsung VR goggle set, and thereafter will allow the patient to use the device freely for up to 30 minutes. Intervals of 2-5 minutes is suggested for first-time use, and patients will be to allowed to discontinue it at any time as long as they are not experiencing any discomfort or side effects (dizziness, motion sickness, etc.). The study staff member will be present at all times, and will work with hospital staff as necessary to ensure the patient is receiving appropriate clinical care throughout the duration of the intervention.

For those patients randomized to the Control, the study staff member will explain that their assignment has been to the standard of care for which is no specific dedicated intervention at this time. Rather their intervention will only be further assessment of their pain scores, vitals, and medication use.

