#### Post-Intervention Procedures

At the completion of either the VR or the Control intervention, the patients will be asked to Quantitative Patient Survey again, this time asking whether the preceding intervention would affect their responses to the questions.

A physician or authorized study staff member will collect blood pressure and pulse rate using standard sphygmomanometers in hospital wards, self-reported pain vitals, and assess coping. Then, the study staff member will ask the patient a series of questions about their experience (See Post-Intervention surveys in Additional Information).

Patients will spend 40 minutes to 1 hour with a member of the study staff during the inpatient stay, including both the initial intervention and interview time. Responses to the qualitative interview will not be audio- or video-recorded; instead, responses will be transcribed and later coded using qualitative data analysis software by study staff. Vitals collected immediately before and after the intervention will be recorded electronically; pain ratings up to 96 hours before and after intervention will be retrieved from the EHR by authorized study staff for analysis. All survey responses will be entered into a secure Redcap on a protected CSHS server.

Between participants, the VR device will be cleaned as detailed below.

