## Post-Intervention Patient Quantitative Survey

### Childbirth Self-Efficacy Inventory

For each of the following behaviors, rate the extent to which you feel having access to the a Virtual Reality intervention would be helpful to you in coping with active labor.

	Not at all helpful				Very helpful
Relax my body.					
Get ready for each contraction.					
Use breathing during labor contractions.					
Keep myself in control.					
Think about relaxing.					
Concentrate on an object in the room to distract myself.					
Keep myself calm.					
Concentrate on thinking about the baby.					
Stay on top of each contraction.					
Think positively.					
Not think about the pain.					
Tell myself that I can do it.					
Think about others in my family.					
Concentrate on getting through one contraction at a time.					
Listen to encouragement from the person helping me.					

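### As written, the post-session survey on how helpful VR would be appears to come before the unblinded post-session pain score; the order should be fixed, with pain first in both arms

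*Combined protocol and SAP*

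**What the plan says.** The primary outcome, in Outcomes and Data Collection, is the fall in pain score from before to after the session. Pre-Intervention Procedures states that patients, providers and staff all know the assignment.

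Post-Intervention Procedures runs in this written order:

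- First paragraph: "At the completion of either the VR or the Control intervention, the patients will be asked to Quantitative Patient Survey again". The patient is to say whether the session just finished would alter her answers.
- Second paragraph: blood pressure and pulse are taken, with "self-reported pain vitals, and assess coping".
- Same paragraph, next sentence: "Then, the study staff member will ask the patient a series of questions about their experience (See Post-Intervention surveys in Additional Information".
- Third paragraph, on data handling: "Vitals collected immediately before and after the intervention will be recorded electronically".

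The form given after the session is the reworded Childbirth Self-Efficacy Inventory in the Post-Intervention Patient Quantitative Survey. For each of 15 behaviours the woman must "rate the extent to which you feel having access to the a Virtual Reality intervention would be helpful to you in coping with active labor". The scale runs from not at all helpful to very helpful. One item is "Not think about the pain". The document contains a single version of this form, for both arms.

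At baseline, Pre-Intervention Procedures has staff take blood pressure and pulse, after which they "will ask the patient to report current pain level on a 0 to 10 scale". Coping follows, and the survey is described last.

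**The concern.** The second half of the primary outcome is an unblinded self-report. If the survey comes first, every woman is asked 15 times about the value of VR just before she rates her pain. The same words are a different prompt in each arm: a VR woman judges something she has just used, and a control woman judges something she was not given. Any effect of the questions on the rating therefore need not cancel between arms.

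The within-arm comparison, on which the sample size is based, is exposed as well. Baseline pain is written as preceding the survey and post-session pain as following it. Even a shift common to both arms would then enter each arm's pre-to-post change.

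There is also delay. The Background rests VR on distraction, and the women are contracting every 5 minutes or more often (Study Population and Period). A pain score taken after a 15-item form describes a later moment than the end of the session.

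**Working it through.** **1. Written order, side by side.**

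- Baseline: blood pressure and pulse, pain, coping, survey.
- After the session: survey, then (next paragraph) blood pressure, pulse, pain, coping, then questions about experience.

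Relative to the pain score, the survey changes sides.

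**2. How firm is the post-session order?** The survey is the only step tied to completion of the session, which favours survey first. The step introduced by *then* concerns the woman's experience, which matches the interview script. Against this, no sequence word joins the first two paragraphs, no clock times are given, and the data-handling sentence puts vitals immediately after the session in a section that counts pain among the vitals. Survey first is the most natural reading, but it is an inference.

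**3. Delay, if the survey is first.** The item count is 15. Assuming 10 to 20 seconds per item (the documents give no figure):

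- 15 × 10 s = 150 s = 2.5 min
- 15 × 20 s = 300 s = 5 min

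With contractions exactly 5 minutes apart, a 2.5-minute window contains the start of one about half the time (2.5/5). A 5-minute window contains one.

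**4. The plan's own figure.** Sample Size Calculations gives 20 per arm for a 13 mm within-group reduction at 5% alpha and 80% power. No SD of change is stated, so 20 cannot be reproduced. Solving backwards with the two-sided normal formula, SD = 13 × √20 / (1.960 + 0.842) = 20.8 mm. The exact paired t test gives 19.7 mm. The figure does not depend on the order of assessments.

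**5. Sensitivity to a differential shift (illustration only).** Take 20 per arm, no true effect, and a shift of b mm in the between-arm difference. The two-sided two-sample t test has 2 × 20 − 2 = 38 degrees of freedom and noncentrality δ = b / (SD × √(2/20)). The false-positive rate is the chance that this noncentral t exceeds the two-sided 5% limit in either direction. At SD 19.7 mm the standard error is 19.7 × 0.316 = 6.23 mm.

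| b (mm) | δ at SD 19.7 | SD 15 | SD 19.7 | SD 25 |
|---|---|---|---|---|
| 0 | 0 | 5.0% | 5.0% | 5.0% |
| 3 | 0.48 | 9.5% | 7.6% | 6.6% |
| 5 | 0.80 | 17.7% | 12.3% | 9.5% |
| 10 | 1.61 | 53.8% | 34.7% | 23.4% |

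The documents support no particular row, and b = 0 is among the possibilities. The table shows only that a trial of this size has little tolerance for a systematic shift in the rating.

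**The case against.** The strongest reply is that the protocol never says the survey comes first. The only sequence word in the section places questions after the pain score, and it points to post-intervention *surveys* in the plural. Two such forms are appended, one quantitative and one qualitative. If both are meant, the VR items follow the pain score and the problem disappears. The sentence about vitals being taken immediately afterwards fits that reading. Nor is paragraph order reliable chronology here: Pre-Intervention Procedures describes consent and baseline measures before it mentions a patient expressing interest and being randomized. The baseline survey is introduced by *additionally*, which is not a sequence word, so the baseline order is partly inferred too.

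This stands as a limit on certainty. It does not remove the point, because the plural reading leaves the opening sentence, which ties the survey to completion of the session, with little work to do. On either reading, the order of assessments around the primary outcome is not fixed.

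A reader might go further and infer that the questions are leading, that both arms' shifts favour VR, or that the woman answers to the person who ran her session. The documents do not support these readings. The scale offers a not-at-all-helpful anchor, although it has no option for harm, and only one of the 15 items names pain. A woman who found VR unhelpful could be moved the other way, the control response to a device she did not use is unknown, and delay could weaken a real effect. The section does not say who gives the repeat survey, and pain may be taken by a physician or any authorized staff member. Both arms already know their assignment, so an effect of question order cannot be separated from ordinary open-label bias.

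**Conclusion.** The point holds in a limited form. The section most naturally places a 15-item VR-focused survey between the end of the session and the post-session pain score, which reverses the written baseline order and sits uneasily with the section's own statement about immediate vitals. Since the primary outcome is unblinded self-report, this is an avoidable possible source of differential reporting, and on this reading a certain source of delay.

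Confidence is moderate that survey first is what staff would follow. The documents support no estimate of the direction or size of any bias. A shift of 3 to 5 mm, which would be 23% to 38% of the 13 mm target (3/13 and 5/13), is purely an assumption, as are the SDs in the table and the seconds per item. A reader might take those figures as evidence that the result will be biased towards VR, but they show sensitivity only. The point is a free improvement in measurement order. The missing SD is a separate matter.

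**What to change.** In Post-Intervention Procedures, state one order for both arms. At the end of the session the 0–10 pain score is taken first, then coping, pulse and blood pressure. Only when these are recorded are the Quantitative Patient Survey and the interview given. Set the REDCap forms in the same order. Pain then precedes the survey at both time points, as baseline is already written, and the statement about immediate vitals becomes consistent with the rest of the section.

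The cost is one reordered paragraph and a matching form order. No procedure, staff or time is added, and sample size, alpha and power do not change.

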### **Outcomes and Data Collection**

Primary Outcome: Reduction in pain scores from pre- to post-intervention

Secondary Outcome:

1. Duration of use of the intervention
2. Acceptability of the intervention
3. Need for IV pain medication during the intervention
  - a. Time to IV pain medication after the intervention
4. Request for an epidural during the intervention
  - a. Time to epidural use after the intervention
5. Vital sign changes during and after the intervention including heart rate and blood pressure.

Data Collection

1. Baseline maternal demographics
  - a. Name and Medical Record Number (secured and stored separate from all other data below)
  - b. Age
  - c. Race/Ethnicity
  - d. Insurance status
  - e. Gravidity/Parity
2. Admitting diagnosis
3. Obstetric data
  - a. Gestational age
  - b. Induction agents
  - c. Mode of delivery
4. Vital Signs (blood pressure, heart rate) before, during (continuous pulse oximeter and blood pressure measurements every 10 minutes) and after the intervention.
5. Pain scores before and after the intervention. Average Pain Rating during 4 hours before intervention, and Average Pain Rating after intervention (up to 24 hours).
6. Pain interventions including time to first use of IV pain medication and first use of epidural.
7. Responses to **Quantitative Patient Survey** (PROMIS Global Health pre-intervention, and modified Childbirth Self-Efficacy Inventory pre- and post-intervention)

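### Unblinded staff, possibly including whoever supervised the headset, may elicit the primary pain score, and the VR-helpfulness survey is listed before it; private self-recording would reduce this avoidable bias.

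*Combined protocol and SAP*

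**What the plan says.** Outcomes and Data Collection defines the endpoint: "Primary Outcome: Reduction in pain scores from pre- to post-intervention". Pre-Intervention Procedures states that "Patients, providers, and study personnel will not be blinded to the assigned intervention".

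The same section describes the two conditions. In the VR arm, "the study staff member will explain the use of the Samsung VR goggle set", and "The study staff member will be present at all times". A Control patient is told that she has standard care, with only further assessment. There is no sham device.

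For the baseline score, a physician or study staff member "will ask the patient to report current pain level on a 0 to 10 scale". For the post-session score, Post-Intervention Procedures says that a physician or study staff member "will collect blood pressure and pulse rate using standard sphygmomanometers in hospital wards, self-reported pain vitals, and assess coping". It does not say whether that score is spoken or written. Neither section requires a collector who took no part in VR delivery, fixes the wording of the question, or has the woman record the number herself.

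Post-Intervention Procedures places the repeat Quantitative Patient Survey first, then vital signs, pain and coping, then the interview. The only printed post-session form (Post-Intervention Patient Quantitative Survey) asks how helpful VR would be for each of 15 coping behaviours.

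**The concern.** The endpoint is a single subjective number at each time point. Blinding the woman to a headset is not possible, so some expectation bias is built into the design. A second source is avoidable: giving the answer face to face to someone who may have just supplied the device and sat through its use. A woman in the VR arm may round her score down out of courtesy. A Control patient has received no device to be polite about. Randomisation does not cancel a reporting shift that arises after assignment and differs by arm.

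The order of assessments may add to this. If the listed order is followed, the woman rates the helpfulness of VR 15 times shortly before she gives the primary score.

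The between-group comparison of change scores would absorb any such shift as apparent benefit. With 20 women per arm, a small average shift is enough to move the error rate.

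**Working it through.** **1. Who collects, and how**

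| Step | Who | How |
|---|---|---|
| Explaining and supervising VR | Study staff member | In person, present throughout |
| Baseline pain score | Physician or study staff member | By asking, 0 to 10 |
| Repeat survey (VR helpfulness) | Not stated | Listed first after the session |
| Post-session pain score | Physician or study staff member | Mode not stated |
| Interview | Study staff member | Spoken, listed last |

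The same person is therefore allowed to deliver VR and take the post-session score, but this is not specified. The baseline score is described before the envelope step. If that order is kept, arm-related reporting bias enters mainly through the post-session score.

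**2. The plan's own sizing**

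Inputs from Sample Size Calculations: alpha 5%, power 80%, a 13 mm within-group reduction, 20 per arm. No SD is given, so the 20 cannot be reproduced from stated inputs. The implied SD of the change can be back-solved, taking alpha as two-sided (an assumption, since the plan does not say):

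- Normal formula: SD = 13 × √20 / (1.960 + 0.842) = 20.8 mm.
- Paired noncentral t, 19 df: SD = 19.7 mm.
- If alpha is one-sided: 23.4 mm (normal) or 22.5 mm (t).

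Because the value depends on the convention, I use a range of 15 to 25 mm and show 19.7 mm within it.

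**3. Effect of an artefactual shift on the between-group t test**

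Assume no true VR effect and a reporting shift of b mm in favour of VR. The standard error of the difference is SD × √(2/20). The noncentrality is b / SE with 38 df, and the two-sided critical value is 2.024. For b = 3 and SD = 19.7, SE = 6.22 and the noncentrality is 3 / 6.22 = 0.48. The chance of a significant result is then 7.6%.

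| Shift b | Share of 13 mm | SD 15 mm | SD 19.7 mm | SD 25 mm |
|---|---|---|---|---|
| 0 mm | 0% | 5.0% | 5.0% | 5.0% |
| 3 mm | 3/13 = 23% | 9.5% | 7.6% | 6.6% |
| 5 mm | 5/13 = 38% | 17.7% | 12.3% | 9.5% |

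On the 0 to 10 scale, taking 10 mm as one point, 3 mm is a mean shift of 0.3 point, for example 6 of 20 women answering one point lower. A 5 mm shift is 0.5 point, or 10 of 20. The shifts are assumed; the documents give no figure for either the total bias or the part due to answering a person.

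**The case against.** A reader might infer that the person who delivers VR does take the score, and takes it aloud. The documents do not say so. They name the study staff member for VR and the interview, but a physician or study staff member for vital signs and pain, so the collector may be someone else. Asking is written only for baseline. The point is about what the plan leaves open.

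A reader might also infer that the bias is confined to one arm. The documents do not establish that. Staff contact of 40 minutes to 1 hour is not limited to VR, and the repeat survey follows either intervention, with only a VR-worded form printed. A net shift towards VR is likely, because only those women used a device, but this is argument and not documented fact.

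It is also fair to say that the error rates in the table do not measure what self-recording would recover. They treat the whole shift as removable. In fact the woman still knows her arm and may expect the team to read her answer. They also carry an SD back-solved from a within-group statement into a between-group test. This objection stands, so the figures are illustrative only.

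Finally, other data exist: pain ratings from the electronic record, and use and timing of IV medication and epidural. These could help show whether a VR effect is credible, so it would be too strong to call a shift undetectable. They are themselves open-label, and none is the primary measure. They do not remove the reason to protect the primary score.

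**Conclusion.** The concern holds as a gap in how the primary outcome is collected. The plan lets unblinded staff, possibly including whoever supervised the headset, elicit the score, and it lists a VR-helpfulness survey ahead of the post-session score. The resulting bias probably favours VR, and its size is unknown. For an assumed SD of 25 down to 15 mm, a 3 mm shift would take the two-sided false-positive rate from 5% to about 7% to 10%, and a 5 mm shift to about 10% to 18%. These results rest on the assumed shifts, the assumed SDs and a two-sided t test with 20 per arm. They should not be read as the trial's actual error rate. The remedy is a cheap, partial improvement and should be adopted; the sample size does not change.

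**What to change.** In Pre-Intervention Procedures and Post-Intervention Procedures, state that in both arms the woman marks the pre- and post-session 0 to 10 score herself, on a paper slip or tablet page with fixed printed wording, out of staff view and without verbal prompt or comment. Move the post-session score ahead of the repeat survey and the interview. Add a sentence that expectation bias remains because she knows her arm, and report it as a limitation.

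The cost is a slip or page and a few protocol sentences, with no added staff. Survey responses already go into a database ("All survey responses will be entered into a secure Redcap on a protected CSHS server"), and the PROMIS form is already worded for marking by the patient. The plan does not show that a bedside tablet is available, so paper is the safe default. The downside is that a woman in labor, contracting at least every 5 minutes, must mark a number rather than say it.

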#### Subject Participation End

The subject's participation will be completed when they wish to discontinue either intervention or at 30 minutes.

#### VR Intervention Details

As previously described, VR interventions have been used as distractions or diversions during medical procedures. This study will be one of the first to test the feasibility of deploying low-cost VR interventions in an obstetric hospital setting. The VR hardware configuration and all software

is currently being developed by AppliedVR, a leader in the development of medical applications for virtual reality technology, including interventions for weight loss and health, safety training, education, and personal development.

### VR Hardware

This study will utilize a Samsung Gear VR goggle set, fitted with a Samsung Galaxy phone that delivers VR images and sound. We have added a sanitary cover to allow patients to use the same goggle set and phone without risk of contamination. Users will wear the VR goggles. Upon beginning their induction, the participants will also be given a brief “quick start” guide that orients them to turning on the unit and choosing modules. A member of the study staff team will then will re-introduce the patients to the hardware on the day of induction.

